## 6.6 Treatment Compliance

The following measures will ensure that the vaccine doses administered comply with those planned, and that any non-compliance is documented so that it can be accounted for in the data analyses:

- All vaccinations will be administered by qualified trial personnel
- The person in charge of product management at the site will maintain accountability records of product delivery to the trial site, product inventory at the site, dose(s) given to each subject, and the disposal of unused or wasted doses

## 6.7 Concomitant Medications and Other Therapies

At the time of enrollment, ongoing medications including other therapies e.g., blood products, should be recorded in the source document as well as new medications prescribed for new medical conditions / AEs during trial participation.

Documentation in the CRB of concomitant medication will be limited to specific categories of medication of interest beginning on the day of vaccination. This may include medications of interest that were started prior to the day of vaccination.

Reportable medications will be collected in the CRB from the day of vaccination to the end of the solicited and unsolicited follow-up period.

Reportable medications include medications that impact or may impact the consistency of the safety information collected after any vaccination and/or the immune response to vaccination. Four categories of reportable medications are defined:

- Category 1: medications impacting or that may have an impact on the evaluation of the safety (e.g., antipyretics, analgesics, non-steroidal anti-inflammatory drugs)
- Category 2: medications impacting or that may have an impact on the immune response (e.g., other vaccines, blood products, antibiotic classes that may interfere with bioassays used by the Global Clinical Immunology [GCI] department, immune-suppressors, immune-modulators with immunosuppressive properties, anti-proliferative drugs such as DNA synthesis inhibitors)
- Category 3: medications impacting or that may have an impact on both the safety and the immune response (e.g., steroids/corticosteroids)
- Category 4: the statin family of anti-hyperlipidemia medications (e.g., atorvastatin, rosuvastatin, simvastatin, pravastatin, and fluvastatin)

The information reported in the CRB for each reported medication will be limited to:

- Trade name or generic name
- Origin of prescription: prophylaxis Yes/No. Medication(s) prescribed for AE prophylaxis will be recorded in the Action Taken of the AE collection tables.
- Medication category
- Start and stop dates

Dosage and administration route will not be recorded. Homeopathic medications, topical and inhaled steroids, and topical, ophthalmic, and ear treatments will not be recorded.

The fact that a medication was given in response to an AE will be captured in the “Action Taken” section of the AE CRF only. No details will be recorded in the concomitant medication CRF unless the medication received belongs to one of the prelisted categories. Medications will not be coded.

## 7 Management of Samples

Blood samples for the assessment of Ab responses will be collected at Visit 1 (D0, pre-vaccination) and at Visit 2 (D28). See the [Table of Study Procedures](#) and [Section 5.1.3](#) for details of the sampling schedule.

### 7.1 Sample Collection

At Visits 1 and 2, 10 mL of blood will be collected in tubes provided by or recommended by the Sponsor. Immediately prior to the blood draw, the staff member performing the procedure will verify the subject’s identity; will verify the assigned subject's number on the pre-printed label that contains that subject’s number and the sampling stage; and will attach the label to the tube. Blood is to be taken from the limb opposite to the one that will be used for vaccination.

### 7.2 Sample Preparation

Detailed instructions on how to prepare blood samples for assessment of Ab response are contained in the Operating Guidelines provided to the site. An overview of the procedures is provided here.

Following the blood draw, the tubes are to be left undisturbed, positioned vertically and not shaken, for a minimum of one hour and a maximum of 24 hours in order to allow the blood to clot. Samples can be stored at room temperature for up to 2 hours; beyond 2 hours, they must be refrigerated at a temperature of +2°C to +8°C after the period of clotting at room temperature and must be centrifuged within a maximum of 24 hours.

After centrifugation, the serum is transferred to the appropriate number of aliquoting tubes. These tubes are pre-labeled with adhesive labels that identify the trial code, the subject’s number, and the sampling stage or visit number.

The subject’s number, the date of sampling, the number of aliquots obtained, the date and time of preparation, and the subject’s consent for future use of his / her samples are to be specified on a sample identification list and recorded in the source document. Space is provided on this list for comments on the quality of samples.

### 7.3 Sample Storage and Shipment

During storage, serum tubes are to be kept in a freezer whose temperature is set and maintained at -20°C or below. The temperature will be monitored and documented on the appropriate form

during the entire trial. If it rises above -10°C for any period of time, the Clinical Logistics Coordinator must be notified. See the Operating Guidelines for further details.

Shipments to the laboratories will be made only after appropriate monitoring, and following notification of the Clinical Logistics Coordinator. Sera will be shipped frozen, using dry ice to maintain them in a frozen state, in the packaging container provided by the carrier. Again, temperatures will be monitored. Shipments must be compliant with the International Air Transport Association 602 regulations.

Samples will be shipped to Global Clinical Immunology (GCI) at Sanofi Pasteur. The address is provided in the Operating Guidelines.

#### **7.4 Future Use of Stored Serum Samples for Research**

Any unused part of the serum samples will be securely stored at the Sanofi Pasteur serology laboratory (GCI) for at least 5 years after the last license approval in the relevant market areas has been obtained for the vaccine being tested.

Subjects will be asked to indicate in the ICF whether they will permit the future use of any unused stored serum samples for other tests. If they refuse permission, the samples will not be used for any testing other than that directly related to this study. If they agree to this use, they will not be paid for giving permission. Anonymity of samples will be ensured. The aim of any possible future research is unknown today, and may not be related to this particular study. It may be to improve the knowledge of vaccines or infectious diseases, or to improve existing tests or develop new tests to assess vaccines. Human genetic tests will never be performed on these samples without specific individual informed consent.

### **8 Clinical Supplies**

Sanofi Pasteur will supply the trial sites with protocols, ICFs, CRBs, SAE reporting forms, diary cards, memory aids, and other trial documents, as well as with the following trial materials: all study vaccines, blood collection tubes, cryotubes, cryotube storage boxes, cryotube labels, temperature recorders, shipping containers, rulers, and digital thermometers.

The means for performing EDC will be defined by Sanofi Pasteur. If a computer is provided by Sanofi Pasteur, it will be retrieved at the end of the trial.

The Investigator will supply all vaccination supplies, phlebotomy, and centrifugation equipment, including biohazard and / or safety supplies. The biohazard and safety supplies include needles and syringes, examination gloves, laboratory coats, sharps disposal containers, and absorbent countertop paper. The site will ensure that all biohazard wastes are autoclaved and disposed of in accordance with local practices. The Investigator will also supply appropriate space in a temperature-monitored refrigerator for the storage of the products and for the blood samples, and appropriate space in a temperature-monitored freezer for serum aliquots.

In the event that additional supplies are required, study staff must contact Sanofi Pasteur, indicating the quantity required. Contact information is provided in the Operating Guidelines.

## 9 Endpoints and Assessment Methods

### 9.1 Primary Endpoints and Assessment Methods

#### 9.1.1 Immunogenicity

##### 9.1.1.1 Immunogenicity Endpoints

The primary endpoints for the evaluation of immunogenicity are:

- HAI Ab titers obtained on D28
- Seroconversion (titer < 10 [1/dil] at D0 and post-injection titer  $\geq$  40 [1/dil] at D28, or titer  $\geq$  10 [1/dil] at D0 and a  $\geq$  4-fold increase in titer [1/dil] at D28)

##### 9.1.1.2 Immunogenicity Assessment Methods

###### *Anti-Influenza Virus Ab Titration by Inhibition of Hemagglutination*

Assays will be performed by the Sponsor's laboratory (GCI, Swiftwater, PA, USA) or at an external testing laboratory under GCI responsibility. The address is provided in the Operating Guidelines.

Test serum samples and quality control sera (sheep, ferret, and/or human sera) are incubated with Sigma Type III neuraminidase from vibrio cholerae to eliminate non-specific inhibitors. Adsorption of spontaneous anti-species agglutinins is then performed by incubating the test serum samples and quality control sera with a red blood cell (RBC) suspension. Following this, the mixtures are centrifuged and the supernatants containing the treated sera are collected for testing. Ten two-fold dilutions (starting at 1:10) of the treated test serum samples and quality control sera are incubated with a previously titrated influenza antigen at a concentration of 4 hemagglutination unit (HAU)/25  $\mu$ L. Influenza antigen is not added to the serum control wells containing only serum and RBCs. The mixture is then incubated and a RBC suspension is added. Following incubation, the results are read. The endpoint of the assay is the highest serum dilution in which complete inhibition of hemagglutination occurred. Each serum sample is titrated in two independent assay runs, and the 2 values, which cannot differ by more than 1 two-fold dilution, are reported. The GMT between the 2 values is calculated at the time of statistical analysis. The lower limit of quantitation (LLOQ) is set at the lowest dilution used in the assay, 1:10. Titers below this level are reported as < 10 (1/dil). If the lowest / first serum dilution used in the assay exhibits complete inhibition of hemagglutination, the serum Ab titer will be reported as < 10 (1/dil). If the highest / last serum dilution used in the assay exhibits complete inhibition of hemagglutination, the serum Ab titer will be reported as  $\geq$  10240 (1/dil).

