#### 9.2.1.2 Immunogenicity Assessment Methods

##### 9.2.1.2.1 Immunogenicity by HAI Method

The immunogenicity assessment methods for the secondary endpoints are the same as those presented in [Section 9.1.1.2](#).

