### 12.3.2 Immunogenicity

In order to appropriately manage replicate values for analysis purposes, the individual GM of all values will be computed for each blood sample after managing extreme values as described. The computed value is then considered the titer for that particular blood sample.

- If a titer is  $< \text{LLOQ}$ , then the computed value,  $\text{LLOQ}/2$ , will be used.
- If a titer is  $\geq \text{LLOQ}$  and  $< \text{ULOQ}$  (or  $\leq \text{ULOQ}$ ), then the titer itself will be used.
- If a titer is  $\geq \text{ULOQ}$  (or  $> \text{ULOQ}$ ), then computed value,  $\text{ULOQ}$ , will be used.

Any other replacement to be applied to specific endpoints will be described in the SAP.

No test or search for outliers will be performed.

No replacement will be done for missing values. Based on the previous TIV-HD and QIV-SD trials in this population, the amount of missing immunogenicity data is expected to be  $\leq 5\%$  in this trial. Usually in vaccine trials, it seems generally reasonable to assume missing immunogenicity data are missing completely at random (MCAR) (13). Indeed, it is highly unexpected that the dropout (or any other reason for missing data) could be linked to the immune response of the subject. Therefore, confirming the results of the PPAS for the primary analysis with the FAS would be satisfactory in terms of sensitivity analysis.

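### HAI reading rules in Protocol 9.1.1.2: the rule for reporting < 10 appears to lack a 'not', and ten two-fold dilutions from 1:10 end at 5120, so the dilution count and the 10240 ceiling disagree

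*Protocol*

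**What the plan says.** All the reading rules stand in one paragraph of Protocol Section 9.1.1.2.

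- Titer: "The endpoint of the assay is the highest serum dilution in which complete inhibition of hemagglutination occurred".
- Lower limit: "The lower limit of quantitation (LLOQ) is set at the lowest dilution used in the assay, 1:10"; titers below it are reported as < 10.
- Low-end reading rule: if the "lowest / first serum dilution used in the assay exhibits complete inhibition of hemagglutination, the serum Ab titer will be reported as < 10".
- Dilution series: "Ten two-fold dilutions (starting at 1:10) of the treated test serum samples".
- High-end reading rule: "If the highest / last serum dilution used in the assay exhibits complete inhibition of hemagglutination", the titer is reported as ≥ 10240.

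These titers feed both primary endpoints in Section 9.1.1.1. The seroconversion definition splits subjects at a baseline titer of 10, beginning "Seroconversion (titer < 10 [1/dil] at D0 and post-injection titer" and continuing with a separate criterion for a baseline of 10 or more. Section 9.2.1.2.1 carries the same assay text to the secondary HAI endpoints: "The immunogenicity assessment methods for the secondary endpoints are the same as those presented in" Section 9.1.1.2.

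Section 12.3.2 substitutes LLOQ/2 below the lower limit and the ULOQ at the ceiling, and "the individual GM of all values will be computed for each blood sample after managing extreme values as described". It gives no numeric HAI ULOQ. The SAP supplied is the ELLA supplement. It too gives no number, and its Section 5.3.1 refers limit handling to a core SAP that was not available for this review.

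**The concern.** Two pairs of statements in that paragraph cannot both be followed.

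**Low end.** Complete inhibition at 1:10 is the finding that makes a titer at least 10, yet the sentence reports that finding as < 10. Under Section 12.3.2 the value would then enter the analysis as 5.

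**High end.** The stated number of dilutions does not reach the stated ceiling. If ten are run as described, a serum that inhibits in every well is known only to be at or above 5120. Entering it as 10240 doubles the recorded value.

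These are the protocol's written rules for reading the titers behind the primary non-inferiority and secondary superiority comparisons, and Section 9.1.1.2 allows an external laboratory to run the assay. What is at stake is the accuracy of recorded titers at the two ends of the scale. The margins, analysis sets, decision rules, and stated sample size and power are not affected.

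**Working it through.** **Low end, by comparing the rules.** Let T be the highest dilution with complete inhibition. If the 1:10 well inhibits completely, then T ≥ 10, and < 10 can only mean that this well did not. The faulty sentence assigns < 10 to the opposite result.

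- Applied to a serum with T = 10, it replaces 10 with 10/2 = 5. The seroconversion threshold does not move: 4 × 10 = 40, the same Day 28 titer as required when baseline is < 10.
- Taken fully literally, it catches every serum with T ≥ 10, because a serum that inhibits at a higher dilution would also be expected to inhibit at 1:10. That would leave the seroconversion category for a baseline of 10 or more empty, so it cannot be intended.

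**High end, the series.** The k-th dilution is 10 × 2^(k−1): 10, 20, 40, 80, 160, 320, 640, 1280, 2560, 5120. The tenth is 10 × 2^9 = 5120. The stated 10240 can be reproduced in two ways:

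- eleven dilutions from 1:10, since 10 × 2^10 = 10240, which contradicts the count of ten; or
- ten dilutions from 1:20, since 20 × 2^9 = 10240, which contradicts the 1:10 start and the lower limit.

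The gap is a factor of 2, or 0.301 on the log10 scale, for a serum at the ceiling.

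**Effect on an arm's GMT if ten dilutions are run and ceiling sera are entered as 10240.** Inputs: log10 SD of 0.63 for A strains and 0.55 for B strains (Protocol Section 12.5); log10-normal titers; Day 28 GMT g of 200 to 800, assumed because the documents give no HAI GMT.

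- Share at or above 5120: f = 1 − Φ((log10 5120 − log10 g)/SD).
- Share at or above 10240: h, the same with 10240.
- Inflation relative to an eleven-dilution assay capped at 10240: 2^(f−h) − 1. Only sera truly between 5120 and 10240 are overstated.
- Inflation relative to a ten-dilution assay capped at 5120: 2^f − 1. This is the upper bound.

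| SD | g | f | h | 2^(f−h) − 1 | 2^f − 1 |
|---|---|---|---|---|---|
| 0.63 | 200 | 0.0127 | 0.0033 | 0.65% | 0.88% |
| 0.63 | 400 | 0.0394 | 0.0127 | 1.87% | 2.77% |
| 0.63 | 800 | 0.1003 | 0.0394 | 4.31% | 7.20% |
| 0.55 | 200 | 0.0052 | 0.0009 | 0.30% | 0.36% |
| 0.55 | 400 | 0.0221 | 0.0052 | 1.17% | 1.54% |
| 0.55 | 800 | 0.0714 | 0.0221 | 3.48% | 5.07% |

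**Effect on the GMT ratio.** The upper-bound shift is 2^(f_QIV − f_TIV) − 1, with g as the TIV-HD GMT. It is zero when the arms are equal. At a true ratio of 1/1.1 the ratio falls by 0.07 to 0.8%. At 1.1 it rises by 0.09 to 0.84%.

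For B-strain superiority (ratio 1.8 and SD 0.55 from Section 12.5; comparator GMT assumed):

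| QIV-HD vs comparator GMT | f, each arm | Upper-bound shift | Shift relative to eleven dilutions |
|---|---|---|---|
| 180 vs 100 | 0.0041, 0.0009 | +0.22% | +0.18% |
| 360 vs 200 | 0.0180, 0.0052 | +0.89% | +0.67% |
| 720 vs 400 | 0.0607, 0.0221 | +2.7% | +1.81% |

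In the last row the recorded ratio is at most 1.8 × 1.027 = 1.85, against a superiority threshold of 1.5.

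**Effect on seroconversion.** A call changes only from a very high baseline. From a Day 0 titer of 2560, a recorded 5120 is a 2-fold rise (no seroconversion) and 10240 is a 4-fold rise (seroconversion). From 1280 the rises are 4-fold and 8-fold, so the call is the same.

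**The case against.** The low-end sentence is a dropped word that its own paragraph corrects. The endpoint definition, the lower limit and the statement about titers below it fix the rule without that sentence, and no competent laboratory would apply it as written. This stands as an argument about impact. It does not make the sentence correct.

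At the high end, ten two-fold dilutions starting at 1:10 could loosely mean ten doubling steps after the 1:10 well, which gives exactly 10240. The description would then be loose and the ceiling right. That is possible, but it is the less literal reading, because the paragraph calls 1:10 the lowest dilution used and so counts it in the series. The documents do not show which number is wrong.

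The consequence also depends on material not seen. Protocol Section 11.2 leaves validation of immunogenicity data to the laboratory's own procedures, and the core SAP may already state the HAI ULOQ. That 10240 would be entered is an inference from its being the only HAI ceiling stated.

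Finally, the percentages rest on assumed GMTs and are bounds only within the range shown. At SD 0.63 the upper-bound formula gives about 0.2% at a GMT of 100 and 14.8% at 1500. The comparison with an eleven-dilution assay is the fairer measure, because entering a serum truly at or above 10240 as 10240 does not overstate it. These caveats are accepted. They support a minor rating and leave both contradictions in place.

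**Conclusion.** Both contradictions are real on the face of the text, and nothing else supplied resolves them. The point is minor.

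- **Low end:** wrong as written, with no effect if the endpoint definition is followed.
- **High end:** count and ceiling differ by one two-fold step, with no effect if eleven dilutions are run. If ten are run and ceiling sera are entered as 10240, arm GMTs rise by 0.3 to 4.3% relative to an eleven-dilution assay, or by at most 0.4 to 7.2% relative to a cap at 5120. Non-inferiority ratios near 1 move by less than 1%. The B-strain superiority ratio rises by at most 0.22 to 2.7%, in the direction that favours superiority.

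The sizes assume log10-normal titers, the protocol SDs, Day 28 GMTs of 200 to 800 (comparator 100 to 400 for superiority), and one recorded value per serum. The effect on seroconversion rates was illustrated for single subjects and not estimated.

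**What to change.** In Protocol Section 9.1.1.2:

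1. Insert the negation, so that < 10 is reported when the first dilution does **not** show complete inhibition.
2. Make the dilution count and the ceiling agree with the validated laboratory method: either ten dilutions from 1:10 with a ceiling of ≥ 5120, or eleven with ≥ 10240.

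Before testing and unblinding, confirm that the same number is the HAI ULOQ applied under Section 12.3.2 and in the core SAP, and state it there if it is absent.

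The cost is two wording corrections and one check against the laboratory method and the core SAP. Nothing operational changes.

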##### 9.1.2 Safety

There are no primary objectives for safety.

### 9.1.3 Efficacy

No clinical efficacy data will be obtained in the trial.

## 9.2 Secondary Endpoints and Assessment Methods

### 9.2.1 Immunogenicity

#### 9.2.1.1 Immunogenicity Endpoints

##### 9.2.1.1.1 Immunogenicity by HAI Method

The secondary endpoints for the evaluation of immunogenicity by HAI method are:

- HAI Ab titers obtained on D0 and D28
- Individual HAI titers ratio D28/D0
- Seroconversion (titer < 10 [1/dil] at D0 and post-injection titer  $\geq$  40 [1/dil] at D28, or titer  $\geq$  10 [1/dil] at D0 and a  $\geq$  4-fold increase in titer [1/dil] at D28)
- Seroprotection (titer  $\geq$  40 [1/dil]) at D0 and D28

##### 9.2.1.1.2 Immunogenicity by SN Method

Neutralizing Ab titers will be measured for each influenza strain with the SN method in a randomly selected subset of subjects from each study group. They will be obtained on D0 and D28.

The secondary endpoints for the evaluation of immunogenicity by SN method are:

- Individual neutralization test (NT) Ab titer on D0 and D28
- Individual NT Ab titer ratio (fold increase in serum NT post-vaccination relative to D0) at D28
- Subjects with NT Ab titers  $\geq$  20 (1/dil),  $\geq$  40 (1/dil),  $\geq$  80 (1/dil) at D28
- Fold-increase in NT Ab titer [post/pre]  $\geq$  2 and  $\geq$  4 at D28
- Detectable NT (NT Ab titer  $\geq$  10 [1/dil]) at D0 and D28

#### 9.2.1.2 Immunogenicity Assessment Methods

##### 9.2.1.2.1 Immunogenicity by HAI Method

The immunogenicity assessment methods for the secondary endpoints are the same as those presented in [Section 9.1.1.2](#).

#### 9.2.1.2.2 Immunogenicity by SN Method

##### *Influenza Virus Neutralization Test*

Assays will be performed by the Sponsor's laboratory (GCI, Swiftwater, PA, USA) or at an external testing laboratory under GCI responsibility.

This NT measures Abs directed against the viral neutralization epitopes of the influenza virus, which may be different from the hemagglutination epitopes, therefore, the NT titers may be different from the HAI titers.

To measure NT, serially diluted, heat-inactivated human serum samples will be pre-incubated with a fixed amount of challenge virus prior to the addition of Madin-Darby canine kidney (MDCK) cells. After overnight incubation, the viral nucleoprotein production in infected MDCK cells is measured by enzyme linked immunosorbent assay (ELISA), using monoclonal Ab specific to either influenza A nucleoprotein or influenza B nucleoprotein. Since serum neutralizing Abs to the influenza virus inhibits the viral infection of MDCK cells, the ELISA optical density results are inversely proportional to the titers of neutralizing Ab present in the serum. The LLOQ is set at the reciprocal of the lowest dilution used in the assay, i.e., 10 (1/dil). Titers below this level are reported as < 10 (1/dil).

